4.5.20 Clinical Outcome Assessments

The SGRQ-C and mMRC will be completed in their entirety by the patient. Each PRO will be collected on paper at the site. Data Collection Methods for Clinical Outcome Assessments PRO instruments will be self-administered at the clinic at specified timepoints during the study (see [Appendix 1](#)). At the clinic, instruments will be administered before the patient receives any information on disease status, prior to the performance of non-PRO assessments, and prior to the administration of study treatment, unless otherwise specified. Copies of each questionnaire are provided in [Appendix 2](#) and [Appendix 3](#).

4.5.20.1 St. George's Respiratory Questionnaire for COPD Patients

The impact of COPD on health and well-being, as measured by the SGRQ-C (Meguro et al. 2007), will be assessed by asking patients to recall their COPD-related experiences and to respond to 40 questions included within three domains: symptoms (7 items), activity (13 items), and impacts (20 items). The SGRQ-C does not specify a recall period, with the exception of the item that assesses chest trouble. This item has a recall period of the past year. Lower scores of the SGRQ-C indicate better health-related quality of life. A copy of the assessment is provided in [Appendix 2](#).

4.5.20.2 Modified Medical Research Council Dyspnea Scale

The mMRC scale assesses dyspnea (Bestall et al. 1999). Patients rate how much their breathlessness impacts their mobility. The mMRC is a 5-item scale. A score of “0” (zero) represents the least impairment due to dyspnea and a score of “4” indicates greatest impairment due to dyspnea. There is no recall period for the mMRC. The mMRC is administered at the site on paper. The mMRC is completed at Visit 1 and Visit 2 to determine whether the patient is eligible for this study. The mMRC is also completed throughout the treatment period as a component of the BODE index, as specified in [Appendix 1](#). A copy of the scale is available in [Appendix 3](#).

4.5.21 Optional Blood Samples

Consenting patients will undergo optional blood samples for DNA extraction to enable SNP array to identify variants that are predictive of response to study drug, are associated with progression to a more severe disease state, are associated with acquired resistance to study drug, are associated with susceptibility to developing adverse events, can lead to improved adverse event monitoring or investigation, or can increase the knowledge and understanding of disease biology and drug safety. Research will be aimed at exploring inherited characteristics. The samples may be sent to one or more laboratories for analysis.

The Informed Consent Form will contain a separate section that addresses optional blood samples. A separate, specific signature will be required to document a patient's agreement to undergo optional blood samples. The investigator should document whether or not the patient has given consent to participate and (if applicable) the date(s) of consent, by completing the appropriate eCRF.

Genomics is increasingly informing researchers' understanding of disease pathobiology. SNP array is a method that sequences specific subsets of the genome, and, along with clinical data collected in this study, may increase the opportunity for developing new therapeutic approaches or new methods for monitoring efficacy and safety or predicting which patients are more likely to respond to a drug or develop adverse events. Data will be analyzed in the context of this study but may also be explored in aggregate with data from other studies. The availability of a larger dataset will assist in identification and characterization of important biomarkers and pathways to support future drug development.

Samples may be used for exploratory biomarker research as described in Section [4.5.18](#). For sampling procedures, storage conditions, and shipment instructions, see the laboratory manual. Refer to Section [4.5.18](#) for details on duration of sample storage, use of samples after patient withdrawal, confidentiality standards for data, and availability of data from biomarker analyses.

4.5.22 Optional Samples for Research Biosample Repository

4.5.22.1 Overview of the Research Biosample Repository

The Research Biosample Repository (RBR) is a centrally administered group of facilities used for the long-term storage of human biological specimens, including body fluids, solid tissues, and derivatives thereof (e.g., DNA, RNA, proteins, peptides). The collection, storage, and analysis of RBR samples will facilitate the rational design of new pharmaceutical agents and the development of diagnostic tests, which may allow for individualized drug therapy for patients in the future.

Samples for the RBR will be collected from patients who give specific consent to participate in this optional research. RBR samples will be analyzed to achieve one or more of the following objectives:

- To study the association of biomarkers with efficacy or disease progression
- To identify safety biomarkers that are associated with susceptibility to developing adverse events or can lead to improved adverse event monitoring or investigation
- To increase knowledge and understanding of disease biology and drug safety
- To study drug response
- To develop biomarker or diagnostic assays and establish the performance characteristics of these assays

4.5.22.2 Approval by the Institutional Review Board or Ethics Committee

Collection, storage, and analysis of RBR samples is contingent upon the review and approval of the exploratory research and the RBR portion of the Informed Consent Form by each site's Institutional Review Board/Ethics Committee (IRB/EC) and, if applicable, an appropriate regulatory body. If a site has not been granted approval for RBR sampling, this section of the protocol (Section 4.5.22) will not be applicable at that site.

4.5.22.3 Sample Collection

The following samples will be stored in the RBR and used for research purposes, including, but not limited to, research on biomarkers related to COPD or other respiratory diseases or drug safety:

- Leftover blood, serum, sputum, and any derivatives thereof (e.g., DNA, RNA, proteins, peptides)

The above samples may be sent to one or more laboratories for analysis of germline or somatic variants via whole genome sequencing (WGS), whole exome sequencing (WES), or other genomic analysis methods. Genomics is increasingly informing researchers' understanding of disease pathobiology. WGS and WES provide a comprehensive characterization of the genome and exome, respectively, and, along with clinical data collected in this study, may increase the opportunity for developing new therapeutic approaches or new methods for monitoring efficacy and safety or predicting which patients are more likely to respond to a drug or develop adverse events.

¹²⁹Xe MRI—Genentech, Inc.

45/Protocol GE42063, Version 5

Data generated from RBR samples will be analyzed in the context of this study but may also be explored in aggregate with data from other studies. The availability of a larger dataset will assist in identification and characterization of important biomarkers and pathways to support future drug development.

For sampling procedures, storage conditions, and shipment instructions, see the laboratory manual.

RBR samples are to be stored until they are no longer needed or until they are exhausted. However, the RBR storage period will be in accordance with the IRB/EC-approved Informed Consent Form and applicable laws (e.g., health authority requirements).

4.5.22.4 Confidentiality

RBR samples and associated data will be labeled with a unique patient identification number.

Patient medical information associated with RBR samples is confidential and may be disclosed to third parties only as permitted by the Informed Consent Form (or separate authorization for use and disclosure of personal health information) signed by the patient, unless permitted or required by law.

Given the complexity and exploratory nature of the analyses of RBR samples, data derived from these analyses will generally not be provided to study investigators or patients unless required by law. The aggregate results of any conducted research will be available in accordance with the effective Sponsor policy on study data publication.

Data generated from RBR samples must be available for inspection upon request by representatives of national and local health authorities, and Sponsor monitors, representatives, and collaborators, as appropriate.

Any inventions and resulting patents, improvements, and/or know-how originating from the use of the RBR data will become and remain the exclusive and unburdened property of the Sponsor, except where agreed otherwise.

4.5.22.5 Consent to Participate in the Research Biosample Repository

The Informed Consent Form will contain a separate section that addresses participation in the RBR. The investigator or authorized designee will explain to each patient the objectives, methods, and potential hazards of participation in the RBR. Patients will be told that they are free to refuse to participate and may withdraw their consent at any time and for any reason during the storage period. A separate, specific signature will be required to document a patient's agreement to provide optional RBR samples. Patients who decline to participate will not provide a separate signature.

The investigator should document whether or not the patient has given consent to participate and (if applicable) the date(s) of consent, by completing the RBR Research Sample Informed Consent eCRF.

In the event of an RBR participant's death or loss of competence, the participant's samples and data will continue to be used as part of the RBR research.

4.5.22.6 Withdrawal from the Research Biosample Repository

Patients who give consent to provide RBR samples have the right to withdraw their consent at any time for any reason. After withdrawal of consent, any remaining samples will be destroyed or will no longer be linked to the patient. However, if RBR samples have been tested prior to withdrawal of consent, results from those tests will remain as part of the overall research data. If a patient wishes to withdraw consent to the testing of his or her RBR samples during the study, the investigator must inform the Medical Monitor in writing of the patient's wishes through use of the appropriate RBR Subject Withdrawal Form and must enter the date of withdrawal on the RBR Research Sample Withdrawal of Informed Consent eCRF. If a patient wishes to withdraw consent to the testing of his or her RBR samples after closure of the site, the investigator must inform the Sponsor by emailing the study number and patient number to the following email address:

[contact]

A patient's withdrawal from this study does not, by itself, constitute withdrawal of consent for testing of RBR samples. Likewise, a patient's withdrawal of consent for testing of RBR samples does not constitute withdrawal from this study.

4.5.22.7 Monitoring and Oversight

RBR samples will be tracked in a manner consistent with Good Clinical Practice (GCP) by a quality-controlled, auditable, and appropriately validated laboratory information management system, to ensure compliance with data confidentiality as well as adherence to authorized use of samples as specified in this protocol and in the Informed Consent Form. Sponsor monitors and auditors will have direct access to appropriate parts of records relating to patient participation in the RBR for the purposes of verifying the data provided to the Sponsor. The site will permit monitoring, audits, IRB/EC review, and health authority inspections by providing direct access to source data and documents related to the RBR samples.

4.6 TREATMENT, PATIENT, STUDY, AND SITE DISCONTINUATION

4.6.1 Study Treatment Discontinuation

Patients must permanently discontinue study treatment if they experience any of the following:

- Any medical condition that the investigator or Sponsor determines may jeopardize the patient's safety if he or she continues to receive study treatment

- Investigator or Sponsor determination that treatment discontinuation is in the best interest of the patient
- Any Grade 4 adverse event that the investigator determines to be related to study treatment

This excludes COPD exacerbations, unless they meet one of the other criteria for study treatment discontinuation.
- Pregnancy
- Development of *C. difficile* diarrhea (*for patients in Cohort A randomized to azithromycin*)
- *Any onset hearing loss, worsening hearing loss, hearing disturbance, or decline in the interpretation of the HHIE-S score (for patients in Cohort A randomized to azithromycin)*

The primary reason for study treatment discontinuation should be documented on the appropriate eCRF. Patients who discontinue study treatment will not be replaced.

Patients will return to the clinic for scheduled study visits after the final dose of study drug (see [Appendix 1](#) for additional details).

4.6.2 Patient Discontinuation from the Study

All patients will return to the clinic for final clinical assessments at Week 48. Patients in Cohort B will be discontinued after completing assessment at Week 48 Visit. Patients in Cohort A will be discontinued from the study after a final safety follow-up assessment performed by telephone at Week 52.

Patients have the right to voluntarily withdraw from the study at any time for any reason. In addition, the investigator has the right to withdraw a patient from the study at any time.

Reasons for patient discontinuation from the study may include, but are not limited to, the following:

- Patient withdrawal of consent
- Study termination or site closure
- Adverse event
- Loss to follow-up
- Patient non-compliance, defined as failure to comply with protocol requirements as determined by the investigator or Sponsor

Every effort should be made to obtain a reason for patient discontinuation from the study. The primary reason for discontinuation from the study should be documented on the appropriate eCRF. If a patient requests to be withdrawn from the study, this request must be documented in the source documents and signed by the investigator. Patients who withdraw from the study will not be replaced.

For Cohort A, participants will be considered to have completed the trial if they complete trial treatment through Visit 7 (Week 48; end-of-treatment visit) and complete Visit 8 (Week 52; safety follow-up visit, which is conducted by telephone).

For Cohort B, participants will be considered to have completed the trial if they continue to participate in the trial through Visit 7 (Week 48).

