Patients who are unable to complete the assessments or meet eligibility requirements during the screening period (from 1 to 28 days) will be permitted to be re-screened once for a total of two times. Patients who re-screen ≤ 6 weeks after Informed Consent Form completion must repeat only the assessments that triggered the screen failure. Patients who re-screen > 6 weeks after Informed Consent Form completion are required to repeat the consent process and all screening assessments except for lung X-rays or HRCT.

[figure not shown]
The first dose of study drug for applicable patients in Cohort A will be self-administered on the same day as randomization (Visit 2, Day 1) after completion of all scheduled assessments. Thereafter, dosing will be repeated once daily during a 48-week treatment period. Patients will continue on stable doses of their SOC therapy, which must include a long-acting bronchodilator inhaler medication (LABAs and/or LAMAs) with or without additional ICS medication throughout the 48-week treatment period and subsequent 4-week safety follow-up period.

The first assessment of the ^{129}Xe MRI intervention will be performed at Visit 2 (Week 0) for all patients randomized to Cohort A and Cohort B and then repeated at Visit 3 (Week 6), Visit 4 (Week 12), Visit 5 (Week 24), and Visit 7 (Week 48). Safety, efficacy, and PRO measures will be assessed throughout the treatment period, as specified in [Appendix 1](#). Patients in Cohort A will be evaluated for safety for an additional 4 weeks following completion of the treatment period.

One or more interim analyses may be executed at the Sponsor's discretion.

[Figure 1](#) presents an overview of the study design. A schedule of activities is provided in [Appendix 1](#).

Figure 1 Study Schema

AEx = acute exacerbations; CB = chronic bronchitis; COPD = chronic obstructive pulmonary disease; GOLD = Global Initiative for Chronic Obstructive Lung Disease; QD = once a day; R = randomization; SFU = safety follow up; SOC = standard of care.

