4.3.2.1 Azithromycin

Patients in Cohort A randomized to treatment intervention will receive generic azithromycin 250 mg taken orally (PO) QD. Patients will receive a 3-month supply of azithromycin 250-mg tablets at Visit 2 (baseline), Visit 4 (Week 12), Visit 5 (Week 24), and Visit 6 (Week 36) at the study site. Patients randomized to receive azithromycin will receive a maximum of 336 doses with a tablet strength of 250 mg. All patients will be provided with a diary to track daily study treatment and the date of any AEx events.

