5.3.1 Adverse Event Reporting Period

Investigators will seek information on adverse events at each patient contact. All adverse events, whether reported by the patient or noted by study personnel, will be recorded in the patient's medical record and on the Adverse Event eCRF.

After informed consent has been obtained but prior to initiation of study randomization, only serious adverse events caused by a protocol-mandated intervention (e.g., invasive procedures such as biopsies, discontinuation of medications) should be reported (see Section 5.3.2 for instructions for reporting serious adverse events).

After randomization, all adverse events will be reported until 28 days after the final dose of azithromycin.

Instructions for reporting adverse events that occur after the adverse event reporting period are provided in Section 5.5.

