5.4.2.2 Events That Occur after Study Treatment Initiation

After initiation of study treatment, serious adverse events and adverse events of special interest will be reported until 28 days after the final dose of study treatment. Investigators should record all case details that can be gathered immediately (i.e., within 24 hours after learning of the event) on the Adverse Event eCRF and submit the report via the electronic data capture (EDC) system. A report will be generated and sent to Safety Risk Management by the EDC system.

In the event that the EDC system is unavailable, the paper Clinical Trial Serious Adverse Event/Adverse Event of Special Interest Reporting Form provided to investigators should be completed and submitted to the Sponsor or its designee immediately (i.e., no more than 24 hours after learning of the event), either by faxing or by scanning and emailing the form using the fax number or email address provided to investigators. Once the EDC system is available, all information will need to be entered and submitted via the EDC system.

Instructions for reporting serious adverse events that occur >28 days after the final dose of study treatment are provided in Section [5.6](#).

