Appendix 1: Schedule of Activities

	Screening	Treatment Period						End of Tx	Safety Follow-Up ^a	ET ^b	UV
		1	2 ^c	3	4	5	6 ^d				
Visit No.		1	2 ^c	3	4	5	6 ^d	7	8 ^e		
Week (Window, days)		0 -28 to -1	(± 4)	6 (± 4)	12 (± 7)	24 (± 7)	36 (± 7)	48 (± 7)	52 (± 7)		
Concomitant medications		x	x	x	x	x	x	x	x	x	x
AEx			x	x	x	x	x	x	x	x	x
Health care utilizations ^{aa}			x	x	x	x	x	x	x	x	x
Adverse events ^{bb}			x	x	x	x	x	x	x	x	x
Study drug Rx (3-month supply) ^{cc}			x		x	x	x				
Patient diary review ^{dd}				x	x	x	x	x			

6MWT = six-minute walking test; AEx = acute exacerbations; BORG CR10 Scale = Borg Category-Ratio 10 Scale[®]; COPD = chronic obstructive pulmonary disease; CT = computed tomography; DL_{CO} = carbon monoxide diffusing capacity; ET = early termination; FEV₁ = forced expiratory volume; HHIE-S = Hearing Handicap Inventory in the Elderly—Screening Questionnaire; HRCT = high-resolution computed tomography; IRB = Institutional Review Board; KCO = carbon monoxide transfer coefficient; mMRC = Modified Medical Research Council; MRI = magnetic resonance imaging; PRO = patient-reported outcome; Rx = prescription; SGRQ-C = St. George's Respiratory Questionnaire—COPD; SNP = single nucleotide polymorphism; SOA = Schedule of Activities; SOC = standard of care; SpO₂ = oxygen saturation; Tx = treatment; UV = unscheduled visit.

^a Safety follow-up will take place via telephone interview for adverse events, health care utilization, and change in medications.

^b The ET visit applies to patients who discontinue study drug prematurely.

^c All baseline assessments at Visit 2 must be completed prior to the first dose of study drug (azithromycin). Azithromycin will only be dispensed to patients randomized to study drug in Cohort A.

^d Patients in Cohort B will be assessed by telephone call from site staff. Assessments limited to changes in concomitant medications, AEx, health care utilizations, and adverse events occurring between Week 24 and Week 36.

^e Limited to patients in Cohort A only.

^f Written informed consent for participation in the study must be obtained before performing any study-specific tests or evaluations.

^g Demographic data will include age (date of birth), sex, and self-reported race/ethnicity.

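### The last Cohort A safety call is timed by study week, so an in-window call can fall 6 to 7 days before the 28-day adverse event period ends

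*Combined protocol and SAP*

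**What the plan says.** Section 3.1 sets the intention: "Patients in Cohort A will be evaluated for safety for an additional 4 weeks following completion of the treatment period". Section 4.6.2 then fixes the last contact by study week: "Patients in Cohort A will be discontinued from the study after a final safety follow-up assessment performed by telephone at Week 52". In Appendix 1, Visit 7 (end of treatment) is Week 48 and Visit 8 is Week 52, each with a window of 7 days either way. Note a describes Visit 8: "Safety follow-up will take place via telephone interview for adverse events, health care utilization, and change in medications". Note e adds: "Limited to patients in Cohort A only".

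Dosing is once daily from the day of randomization for 48 weeks (Section 3.1). Section 4.3.2.1 caps it: "Patients randomized to receive azithromycin will receive a maximum of 336 doses with a tablet strength of 250 mg".

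The reporting period is defined from the last dose. Section 5.3.1: "After randomization, all adverse events will be reported until 28 days after the final dose of azithromycin". For the more important events, Section 5.4.2.2 says that "serious adverse events and adverse events of special interest will be reported until 28 days after the final dose of study treatment".

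Nothing in the protocol links the date of Visit 8 to the last dose, sets a minimum interval between them, or schedules a contact after Visit 8.

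**The concern.** Two clocks are in use. The reporting period runs from the last dose, while the final call runs from randomization with a symmetric window. On the nominal dates they agree, but on the early side of the window the call comes before the reporting period has ended.

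Section 5.3.1 has investigators ask about adverse events whenever they are in contact with the patient, and Visit 8 is the last scheduled contact. After an early call, events in the remaining days reach the site only if the patient volunteers them or the site hears of them some other way. Comparing the safety of azithromycin plus SOC with SOC alone is a stated objective (Section 2.2). The gap concerns active questioning about events; the rule on what must be reported is not affected.

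**Working it through.** Inputs: once-daily dosing from the day of randomization for 48 weeks (Section 3.1); a cap of 336 doses (Section 4.3.2.1); Visits 7 and 8 at Weeks 48 and 52, each ±7 days (Appendix 1); a reporting period of 28 days after the last dose (Sections 5.3.1 and 5.4.2.2).

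**The plan's own figure.** 48 × 7 = 336 doses, which reproduces the cap.

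**Full adherence.** The protocol does not say how Week 52 maps to a day number, so both conventions are shown.

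| | Randomization = day 0 | Randomization = Day 1, Week 52 = Day 364 |
|---|---|---|
| Last (336th) dose | day 335 | Day 336 |
| End of 28-day period | 335 + 28 = 363 | 336 + 28 = 364 |
| Visit 8 window | 364 ± 7 = 357 to 371 | 364 ± 7 = 357 to 371 |
| Last dose to earliest call | 357 − 335 = 22 days | 357 − 336 = 21 days |
| Shortfall | 28 − 22 = 6 days | 28 − 21 = 7 days |
| Last dose to nominal call | 364 − 335 = 29 days | 364 − 336 = 28 days |
| Last dose to latest call | 371 − 335 = 36 days | 371 − 336 = 35 days |
| Window days under 28 days post-dose | 357 to 362: 6 of 15 | 357 to 363: 7 of 15 |

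The remaining steps use randomization = day 0.

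**Late Visit 7.** The latest Visit 7 is day 336 + 7 = 343. If the last dose were taken that day and Visit 8 were at its earliest, the interval would be 357 − 343 = 14 days. Uninterrupted dosing to day 343 would be 344 doses, 8 above the cap, so this needs about 8 missed doses to be made up. The documents do not say whether that is allowed. It is an outer bound, and the finding does not rest on it.

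**Early Visit 7.** The earliest Visit 7 is day 336 − 7 = 329. If azithromycin stops on that day, the earliest call is 357 − 329 = 28 days later and there is no shortfall. If the patient keeps taking tablets to the cap, the last dose is still day 335 and the 22-day figure stands.

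**The case against.** The strongest reply is that the planned schedule is right. The nominal Week 52 call falls 28 to 29 days after the last dose, and Section 3.1 can be read as already requiring four weeks of safety evaluation after treatment. That is fair as to intent, but a site working from Appendix 1 can comply fully and still call at 21 to 22 days.

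Second, reporting is not cut short. The 28-day duty stands whatever the call date, and unscheduled visits also collect adverse events. Sections 5.5.1 and 5.6 add follow-up of known events and notification of later related serious events. This stands, and it limits the consequence. None of it provides a scheduled question in the uncovered days.

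Third, Visit 7 is labelled the end-of-treatment visit, so an early Visit 7 may end dosing early. With the last dose on the visit day, that closes the gap completely only at the earliest permitted Visit 7, day 329; at day 332, for example, the earliest call would be 357 − 332 = 25 days later.

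Fourth, the benefit is small. Section 5.1.2.5 notes that *C. difficile* diarrhea can appear more than 2 months after antibiotics, so a day-28 call would not fully cover that risk. This is true, but 28 days is the period the sponsor chose, and the call should at least reach its end.

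**Conclusion.** The point holds. With full adherence, a compliant call can come 21 to 22 days after the last azithromycin dose, 6 to 7 days before the reporting period ends; the one-day spread reflects only how days are counted. It rests on once-daily dosing to the 336-dose cap and on the Visit 8 window in Appendix 1.

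The number of patients affected cannot be estimated, because the documents do not show where in the window calls will be made. The ceiling is the azithromycin arm, about 100 / 2 = 50 patients, less those who stop early and so have a longer interval. The SOC arm has no last azithromycin dose, so the shortfall does not apply to it in this form. The primary and secondary endpoints are not affected. This is worth considering as a low-cost improvement to safety follow-up.

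**What to change.** In Appendix 1, set Visit 8 at 28 days (+7/-0) after Visit 7 or after the last azithromycin dose taken up to the end of treatment, whichever is later. In the Cohort A SOC arm, set it at 28 days (+7/-0) after Visit 7. The later-of-the-two rule is needed because an early Visit 7 (day 329) can precede the last dose (about day 335). It also covers patients who stop azithromycin early but stay in the study, whose call would be timed from Visit 7.

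Amend both mentions of Week 52 in Section 4.6.2, and check the 52-week statements in the synopsis and Sections 3.1 and 3.2 for consistency.

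Costs:
- The call already exists, but its window narrows from 15 days to 8, so somewhat more calls may fall out of window.
- Some calls move later. With Visit 7 on day 343, the earliest permitted call moves from day 357 to 343 + 28 = 371 (14 days), and the latest from day 371 to 343 + 35 = 378 (7 days). The last-patient-last-visit date could move accordingly.
- An amendment is required. The sponsor would need to decide whether it counts as logistical or administrative under Section 9.7 or needs prior approval.
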